APPENDIX IV. BLOOD SAMPLING AND SHIPPING INSTRUCTIONS

Blood collection procedure

Blood and urine samples will be collected, handled, and processed according to the instructions provided in the Central Laboratory Manual.

Sample shipping guide from the study center to the central laboratory

Samples will be shipped from the study center to the central laboratory on the day of collection or as specified in the laboratory manual. The central laboratory will provide packaging, labeling, and shipping instructions.

APPENDIX V. SUMMARY ADAPTED FROM GUIDELINES OF THE US MULTI-SOCIETY TASK FORCE ON COLORECTAL CANCER AND OTHER COLONOSCOPY REQUIREMENTS

Note: Patient may be enrolled if no follow-up colonoscopy after polyp removal is due while participating in the study.

[figure not shown]
1. Patients age 50 years (40 years if African American) and older must have had a colonoscopy with negative findings within the 10 years prior to the Screening Visit (Visit 1).
2. If the most recent colonoscopy revealed hyperplastic polyps that were entirely removed, the patient may be enrolled, provided the colonoscopy was performed within 10 years prior to the Screening Visit (Visit 1).
3. If the most recent colonoscopy revealed 2 or fewer small (≤ 1 cm) adenomatous polyps with tubular structure with low grade dysplasia and without appreciable villous tissue, the patient may be enrolled, provided the colonoscopy was performed within 5 years prior to the Screening Visit (Visit 1).
4. Patients who have 1 first-degree relative with colorectal cancer or adenomatous polyps diagnosed *before age 60* or 2 first-degree relatives with colorectal cancer diagnosed at any age must have had a colonoscopy with negative findings 5 years before the Screening Visit (Visit 1). This applies to patients who are 40 years or older and to patients younger than 40 years, who are 10 or fewer years from the age at which their youngest relative was found to have 1 of the aforementioned conditions.
5. Patients who have 1 first-degree relative with colorectal cancer or adenomatous polyps diagnosed at *age 60 or older* or 2 second-degree relatives with colorectal cancer diagnosed at any age must have had a colonoscopy with negative findings within 10 years prior to the Screening Visit (Visit 1). This applies to patients who are 40 years or older and to patients younger than 40 years, who are 10 years or fewer years from the age at which their youngest relative was found to have 1 of the aforementioned conditions.

Other Colonoscopy Requirements:

Patients of any age who have alarm symptoms must have had a colonoscopy with negative findings after the onset of the alarm symptoms and within 5 years prior to the Screening Visit (Visit 1). Alarm symptoms include lower GI bleeding (rectal bleeding or heme-positive stool), iron-deficiency anemia, and weight loss. (Note: Current unexplained or clinically significant alarm symptoms are exclusionary.)

These requirements are adapted based on recent Guidance on Colorectal Cancer Screening ([Levin et al, 2008](#); [Lieberman et al, 2012](#); [Quaseem et al, 2012](#)).

Rationale: A new section has been added to introduce the possibility that some patients' ADAs may not have reverted to baseline at the 4-Month Follow-up Visit; an additional visit (Visit 11) will be required for those patients.

The new section will read as follows:

[REDACTED]

[REDACTED]

■ [REDACTED]

■ [REDACTED]

■ [REDACTED]

■ [REDACTED]

5.0 **REVISIONS**

5.1 **SECTION 2.0 SYNOPSIS AND SCHEDULE OF
EVALUATIONS (PAGE 2)**

[figure not shown]
[REDACTED]

[figure not shown]
[REDACTED]

[figure not shown]
[REDACTED]

[REDACTED]

[REDACTED]

[REDACTED]

[REDACTED]

[REDACTED]

[REDACTED]

5.3 SECTION 9.3.1, INCLUSION CRITERIA (PAGE 25)

Rationale: Inclusion criterion 9 that addresses language fluency had previously been attached in error to the end of inclusion criterion 8.

The last sentence of inclusion criterion 8 becomes inclusion criterion 9 as follow:

[REDACTED]

- | [REDACTED]
- | [REDACTED]

5.6 SECTION 9.5.4.6, IMMEDIATE REPORTING OF SERIOUS ADVERSE EVENTS (PAGE 44)

Rational: This section has been amended to update the Sponsor's Study Physician Medical Emergency phone number.

The last paragraph of this section now reads as follow:

Sponsor's Study Physician Medical Emergency phone number: [REDACTED]
[REDACTED]

- [REDACTED]
- [REDACTED]
- [REDACTED]

[REDACTED]

- [REDACTED]
- [REDACTED]

[REDACTED]

4.1 Study Design Summary

This will be a multicenter, open-label, long-term clinical study to assess the immunogenicity and long-term safety of linaclotide administered orally to adult participants with irritable bowel syndrome with constipation (IBS-C) and chronic idiopathic constipation (CIC), and to evaluate lower doses of linaclotide in participants who consider study withdrawal due to intolerable adverse events (AEs) that may be related to the use of linaclotide. Approximately 800 IBS-C or CIC participants (a minimum of 300 each) will be enrolled.

The study will consist of up to a 3-week Screening Period, followed by a 52-week Treatment Period (Figure 4–1). Participants who meet the entry criteria will receive once daily, open-label doses of 290 μ g linaclotide for participants with IBS-C; those with CIC will receive once daily, open-label doses of 145 μ g linaclotide.

In order to limit participant withdrawals from the study due to AEs and to gain information about the effect of lowering the dose in participants who experience intolerable AEs (defined as AEs that subjectively would cause a participant to consider study withdrawal), in particular diarrhea and other gastrointestinal (GI) AEs that may be related to the use of linaclotide, the following intervention (Figure 4-2) will be offered as an optional treatment course to such participants, unless deemed clinically inappropriate by the Investigator:

1. A temporary suspension of dosing of up to 7 days. If the dose suspension needs to last longer than 7 days because the intolerable AE has not resolved, then the Investigator should contact the Study Physician to discuss the duration of the dose suspension or withdrawal of the participant from the study. All AEs resulting in the temporary suspension will be recorded on the electronic case report form (eCRF).

2. After the intolerable AE has resolved, the participant will be randomized into a Double-blind Treatment Period via an interactive Web response system (IWRS) and will receive dose regimens specific to each indication as follows. If the randomized dose regimen is tolerated, the participant will remain on this dose for the duration of the study (total duration of linaclotide exposure [whether open-label or double-blind] is not to exceed 52 weeks).

IBS-C participants will be randomized in a 1:1:1 ratio to 1 of the following regimens:

- Linaclotide 290 µg every day
- Linaclotide 145 μg every day
- Linaclotide 72 µg every day

CIC participants will be randomized in a 1:1 ratio to 1 of the following regimens:

- Linaclotide 145 μg every day
- Linaclotide 72 µg every day
- 3. If, after randomization, participants experience intolerable AEs, in particular diarrhea or other GI AEs, the dosing should be temporarily suspended for up to 7 days. If the dose suspension needs to last longer than 7 days because the intolerable AE has not resolved, then the Investigator should inform the Study Physician about the duration of dose suspensions or withdrawal of the participant from the study.
 - After the intolerable AE has resolved, irrespective of the IBS-C or CIC status, participants should be dispensed open-label linaclotide (72 μ g) and may continue on this dose in a Dose-reduced Open-label Treatment Period for the duration of the study.
- 4. If participants experience an intolerable AE while receiving the adjusted dose of 72 μg in the Dose-reduced Open-label Treatment Period, study participation should be terminated.
- 5. In the event of a planned procedure or an AE during which a participant requires dose suspension longer than 7 days, the Investigator should inform the Study Physician about the duration of dose suspensions. Upon event completion or AE resolution, the participant should be resumed on the assigned dose.

4.2 Study Objectives and Endpoints

Each study objective is presented with corresponding endpoint(s) below:

Table 4–1 Study Objectives

Objectives	Endpoints		
Primary			
To assess the potential of linaclotide treatment to induce the development of anti-drug antibodies (ADAs)	Treatment-related ADA positive responder		
Secondary			
To provide additional evidence supporting the long- term safety of linaclotide in adult IBS-C and CIC participants	 Adverse Events Clinical Laboratory Assessments Vital Signs Electrocardiograms Immunogenicity 		
To provide additional evidence supporting the long- term efficacy of linaclotide in adult IBS-C and CIC participants	 Patient assessment of constipation severity Patient assessment of IBS symptom severity (IBS-C only) Degree of relief of IBS symptoms (IBS-C only) IBS treatment satisfaction assessment (IBS-C only) Constipation treatment satisfaction assessment (CIC only) 		
To evaluate lower doses of linaclotide in participants who consider study withdrawal due to intolerable AEs	 Recurrence of diarrhea Recurrence of intolerable diarrhea Time to first recurrence of diarrhea Time to first recurrence of intolerable diarrhea 		

5. Statistical Methodology and Study Endpoints

5.1 Statistical Methods Planned in the Protocol and Determination of Sample Size

This statistical analysis plan (SAP) expands the statistical section of the protocol and contains a detailed description of methods to analyze data collected in the study. The text portion of the SAP will be included in the CSR report as Appendix 16.1.9.

5.1.1 Statistical and Analytical Plans

Statistical analyses will be conducted using SAS Version 9.3 or newer.

5.1.1.1 Common Conventions

5.1.1.1.1 Analysis Populations

The analysis populations will consist of participants as defined below:

Table 5–1 Analysis Populations

Population	Definition	Study Treatment
Screened	All screened participants who sign an ICF for the study and receive a participant identification number (PID)	_
	 Rescreened participants considered separately for each unique PID 	
All enrolled	All Screened Population participants who continue into the	Indication
participants	Open-label Treatment Period per the screening disposition eCRF	
	 This population will be used for selected listings only 	
	and is not considered a formal analysis population	
Safety	All Screened Population participants who receive ≥ 1	Indication
	administration of study treatment	
Intent-to-Treat (ITT)	All Safety Population participants with ≥ 1 postbaseline	Indication
	assessment for any efficacy or health outcomes parameter during	
	the Treatment Period, fully described in Section 5.1.1.3	
	 Patient assessment of constipation severity 	
	 Patient assessment of IBS symptom severity (IBS-C only) 	
	 Degree of relief of IBS symptoms (IBS-C only) 	
	• IBS treatment satisfaction assessment (IBS-C only)	
	 Constipation treatment satisfaction assessment (CIC 	
	only)	
Randomized	All Safety Population participants who are randomized to double-	Randomized assignment
	blind study treatment following resolution of an intolerable AE	Č
Double-blind Safety	All Randomized Population participants who receive ≥ 1	Randomized assignment
•	administration of study treatment during the Double-blind	-
	Treatment Period	

Population	Definition	Study Treatment
Double-blind ITT	All Double-blind Safety Population participants with ≥ 1 post- randomization assessment for any efficacy or health outcomes parameter during the Double-blind Treatment Period, fully described in Section 5.1.1.3 • Patient assessment of constipation severity • Patient assessment of IBS symptom severity (IBS-C only) • Degree of relief of IBS symptoms (IBS-C only) • IBS treatment satisfaction assessment (IBS-C only) • Constipation treatment satisfaction assessment (CIC only)	Randomized assignment

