9.3.3 Removal of Patients from Therapy or Assessment

A premature discontinuation will occur when a patient who signed the ICF ceases participation in the study, regardless of circumstances, before the completion of the study. Patients can be prematurely discontinued from the study for one of the following reasons:

- Screen failure (failure to meet inclusion/exclusion criteria)
- Withdrawal of consent
- AE
- Lack of efficacy
- Protocol violation
- Noncompliance with investigational product
- Lost to follow-up
- Study terminated by Sponsor
- Site terminated by Sponsor
- Other

All enrolled patients who prematurely discontinue from the study, unless the cause is screen failure, must be seen for a final assessment at ET, and follow-up blood samples as described in the Schedule of Evaluations ([Section 2.0](#)) should be obtained for patients who are ADA positive at the last visit. A *final assessment* will be defined as completion of the evaluations scheduled for the Final Visit at the end of Week 52 End of Study (EOS)/ET Visit (Visit 8).

Any patient who withdraws because of an AE will be followed until the AE resolves, stabilizes, or can be explained as being unrelated to investigational product. The study centers must make a reasonable effort to follow pregnant patients until delivery or end of the pregnancy.

Patients who do not complete all required scheduled visits/procedures must be requested in writing to come in for an ET Visit and to return any unused investigational product. A clear description of premature discontinuation must be documented. A copy of the letter, together with the source documentation, will be kept by the Investigator. The reasons for premature discontinuation from the study will be reflected on the eCRF.

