9.7 STATISTICAL METHODS AND DETERMINATION OF SAMPLE SIZE

9.7.1 Patient Populations

The following populations will be considered in the statistical analysis of the study.

9.7.1.1 *Screened Population*

The Screened Population will consist of all patients who sign an ICF for the study and receive a patient identification number.

9.7.1.2 *Safety Population*

The Safety Population will consist of all patients in the Screened Population who receive at least 1 dose of investigational product during the Treatment Period.

9.7.1.3 ***Intent-to-Treat Population***

The Intent-to-Treat (ITT) Population will consist of all patients in the Safety Population who have at least 1 postbaseline assessment for any efficacy or health outcomes parameter.

9.7.1.4 ***Randomized Population***

The Randomized Population will consist of all patients in the Safety Population who are randomized to double-blind investigational product following resolution of an intolerable AE.

9.7.1.5 ***Double-blind Safety Population***

The Double-blind Safety Population will consist of all patients in the Randomized Population who receive at least 1 dose of investigational product during the Double-blind Treatment Period.

9.7.1.6 ***Double-blind ITT Population***

The Double-blind ITT Population will consist of all patients in the Double-blind Safety Population who have at least 1 post-randomization assessment for any parameter during the Double-blind Treatment Period.

9.7.2 **Patient Disposition**

The number of patients in each of the study populations described in Section 9.7.1 will be summarized overall, by indication (IBS-C or CIC), and study center.

The number of screen failures (ie, patients who enter the Screening Period but not the Treatment Period) along with the associated reasons for failure will be tabulated overall.

The number and percentage of patients in the categories described in Table 9.7.2-1 will be summarized overall and by treatment group, if specified, for each indication in the Safety Population.

Table 9.7.2-1. Summarization of Patient Disposition

Category	By Treatment Group
Patients who complete the Open-label Treatment Period	No
Patients who prematurely discontinue during the Open-label Treatment Period	No
Reasons for premature discontinuation of open-label treatment as recorded on the eCRF	No
Patients who prematurely discontinue open-label treatment due to AE who do not randomize to double-blind treatment	No

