5.1.1.1.5 Treatment Periods

The non-overlapping Open-label, Double-blind, and Dose-reduced Open-label treatment periods are defined by their respective treatment start and end dates. These 3 treatment periods are subsets of the overall Treatment Period. The start and end dates for each period are defined as follows:

Table 5–5 Treatment Period Definitions

Parameter	Start	End
Treatment Period	Treatment start date = first dose date of any	Treatment end date = last dose date of any
	LIN treatment	LIN treatment
Open-label	Open-label start date = first dose date of open-	Open-label end date = last dose date of open-
Treatment Period	label LIN treatment	label LIN treatment
	 Identical to treatment start date 	 Identical to treatment end date for
		participants who do not enter the
		Double-blind Treatment Period
Double-blind	Double-blind start date = first dose date of	Double-blind end date = last dose date of
Treatment Period	double-blind LIN treatment	double-blind LIN treatment
		 Identical to treatment end date for
		participants who do not enter the
		Dose-reduced Open-label Treatment
		Period

¹ Highest LIN dose by indication: IBS-C: LIN 290 μg; CIC: LIN 145 μg.

² Lower LIN doses by indication: IBS-C: LIN 72 μg, LIN 145 μg; CIC: LIN 72 μg.

Dose-reduced	Dose-reduced open-label start date = first dose	Dose-reduced open-label end date = last dose
Open-label	date of dose-reduced open-label LIN	date of open-label LIN treatment
Treatment Period	treatment	 Identical to treatment end date

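### The SAP's ITT definition stops counting scores at the last dose, so a patient scored only at a later early termination visit is in the protocol's ITT but not in the SAP's

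*SAP*

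**What the plan says.** **ITT.** Protocol 9.7.1.3 takes Safety Population patients "who have at least 1 postbaseline assessment for any efficacy or health outcomes parameter" and sets no date limit. SAP Table 5-1 starts the same way ("All Safety Population participants with ≥ 1 postbaseline") but ties the assessment to "the Treatment Period, fully described in Section 5.1.1.3". Table 5-5 closes that period at the final dose: "Treatment end date = last dose date of any" linaclotide treatment.

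**ET visit.** Protocol 9.3.3 says that enrolled patients who discontinue "must be seen for a final assessment at ET", with the evaluations scheduled for Week 52. Protocol 9.5.1.1 allows the discontinuation blood sample up to 7 days after the last dose. The first scheduled postbaseline efficacy score is at Week 2 (SAP Table 5-13).

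**Windows elsewhere in the SAP.** Postbaseline ADA status runs to 7 days after the treatment end date (5.1.1.4.6). Treatment-emergent events run to 1 day after it (Table 5-20). The ITT row has no allowance.

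**Double-blind ITT.** SAP Table 5-1 asks for a post-"randomization assessment for any efficacy or health outcomes parameter during the Double-blind Treatment Period". Table 5-5 again closes the period at the final dose ("Double-blind end date = last dose date of" double-blind treatment). Protocol 9.7.1.6 has the same period limit but accepts an assessment of any parameter. SAP 5.1.1.3.3 runs the double-blind analyses in the Double-blind Safety Population unless otherwise specified, and the History of Change records that move for selected analyses. The demographic and baseline tables by dose (5.1.1.2.4 and 5.1.1.2.5) remain on Double-blind ITT.

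**The concern.** The SAP presents itself as expanding the protocol's statistical section, yet its ITT set is narrower than the protocol's, and no visible entry in the History of Change records the narrowing. The patients at risk of removal are not a random sample. They stopped in the first two weeks and gave their only postbaseline score on the way out.

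At stake are the descriptive efficacy summaries and the ITT demographic and baseline tables. The last of these matters slightly more than it seems, because Table 5-10 summarises baseline efficacy in the ITT Population only. A patient removed from ITT therefore has no efficacy data in any of these tables, before or after treatment.

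In the double-blind phase the question is whether the patients described by dose at baseline are the same patients in whom recurrence of diarrhea is analysed.

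**Working it through.** **The plan's own figure.** The only stated figure is the one-sided 95% upper limit for 0/800: 1 − 0.05^(1/800) = 0.3738%, which reproduces the 0.374%. It does not depend on ITT, because the ADA analysis uses patients with an assessable postbaseline sample.

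**The definitions applied to one patient.** Suppose the last dose is on Day 8 and the ET visit, with efficacy scores, is on Day 12.
- Protocol 9.7.1.3: one postbaseline score exists, so the patient is in ITT.
- SAP Tables 5-1 and 5-5: the Treatment Period ended on Day 8, no Week 2 score exists, and the Day 12 score is outside the period. The patient is not in ITT.
- If the last dose had been taken on the ET date, both definitions would include the patient.

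**How many.** The documents give no count, so this is an illustration. Let N be planned enrolment, d the share discontinuing, s the share of those stopping before Week 2, and q the share of those whose scored ET visit falls after the last dose.

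Affected = N × d × s × q

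- N = 800 (Protocol synopsis; SAP 4.1).
- d = 5%, borrowed from Protocol 9.4.4, which gives it for diarrhea discontinuation in the pivotal studies.
- s = 50%, an assumption. Section 9.4.4 dates the onset of diarrhea, mostly within 2 weeks, and not the stopping of treatment.
- q = 50% to 100%, an assumption.

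Results with d = 5%:
- s = 50%: 800 × 0.05 × 0.50 × 0.50 = 10 (1.25%), up to 800 × 0.05 × 0.50 × 1.00 = 20 (2.5%).
- s = 25%, q = 50%: 5 patients (0.62%).
- s = 75%, q = 100%: 30 patients (3.75%).

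If discontinuation for any reason were 20%, with s = 75% and q = 100%, the count would be 800 × 0.20 × 0.75 = 120 (15%). That is an extreme corner, not an expectation.

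**Effect on a mean.** If a fraction p of the patients contributing to a visit is removed, and their mean change differs from that of the others by D points, the visit mean moves by p × D. For an assumed D of 1 point and p of 1.25% to 2.5%, the shift is 0.0125 to 0.025 points on a 5-point scale. Table 5-3 counts only patients with values at baseline and at that visit, so each removed score can affect only the visit to which it is assigned.

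**Double-blind ITT, side by side.**
- Period limit: present in both documents.
- Qualifying assessment: any parameter (protocol); efficacy or health outcomes, with five scores listed (SAP).
- Consequence: Protocol 9.7.5 lists recurrence of diarrhea among the parameters analysed in Double-blind ITT. A patient with a recurrence but no in-period score can therefore qualify under the protocol's wording and not under the SAP's.

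**The case against.** The strongest reply is that the literal reading may not be the intended one. Protocol 9.5.1.1 treats the ET visit as the end of the Treatment Period for ADA follow-up. SAP Section 6.2 (analysis visits) and parts of 5.1.1.3 are not shown, and they may handle ET scores. This stands as a caution. But assigning scores to visits would not by itself restore a patient whom Table 5-1 keeps out of the population.

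Second, an on-treatment limit can be defended. The severity and relief items look back 7 days. With a last dose on Day 8 and a score on Day 12, 3 or 4 of the 7 days are off drug, depending on whether the visit day counts. This is a fair reason to choose such a limit openly, but not to leave it as an unrecorded departure from the protocol.

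Third, nothing says that ET usually follows the last dose; the 7 days is a maximum, and only for the blood sample. The 5% comes from earlier studies, whereas this trial offers suspension and randomization to keep patients in. Those who continue can be scored later and enter ITT. Both points stand, which is why the count is only an illustration.

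Finally, Protocol 9.7.3 itself names Double-blind ITT for the double-blind demographic and baseline tables. That also stands: the SAP is not in breach there, and the case for adding tables rests on its later change of analysis population.

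**Conclusion.** The ITT mismatch is real and should be settled, but it is small. On the stated assumptions it concerns about 10 to 20 of 800 patients (1.25% to 2.5%), fewer if some are randomized and scored later. It slightly affects an early-visit mean in summaries that carry no inferential tests, along with the ITT demographic and baseline tables. The ADA endpoint is unaffected.

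A reader might infer more, and the documents do not support it:
- **That the SAP added the period limit to Double-blind ITT.** Protocol 9.7.1.6 already has it. The SAP's change is the narrower kind of assessment.
- **That all 40 patients (5% of 800) would be lost before Week 2.** The protocol dates the onset of diarrhea, not discontinuation, and gives no basis for that bound.
- **That the rule biases the dose comparison of recurrence.** In the visible SAP those analyses use Double-blind Safety, and Double-blind ITT serves only the demographic and baseline tables. The most that follows is that these tables may describe a different set of patients.

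**What to change.** 1. In the ITT row of SAP Table 5-1, delete the Treatment Period limit, or extend it to include the Week 52/ET visit, so that it matches Protocol 9.7.1.3. Naming the visit is safer than borrowing the 7-day ADA window: Protocol 9.3.3 lets an ET visit follow a written request and sets no 7-day limit for efficacy scores.
2. Reconcile the qualifying assessment for Double-blind ITT between Protocol 9.7.1.6 and SAP Table 5-1, and record the decision in the History of Change.
3. Also present the double-blind demographic and baseline tables for the Double-blind Safety Population.

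The cost is a few lines of SAP wording and one more set of tables, with no new data. The downside is that some ET scores will have a recall period that partly covers days off drug; a table footnote can say so.
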